## 6.12 Infusion Guidelines for Pembrolizumab

Signs and symptoms usually develop during or shortly after drug infusion and generally resolve completely within 24 hours of completion of infusion.

Table 18 shows treatment guidelines for patients who experience an infusion reaction associated with administration of pembrolizumab (MK-3475).

**Table 18: Management of pembrolizumab-associated infusion-related reactions**

NCI CTCAE Grade	Treatment	Premedication at subsequent dosing
Grade 1: Mild reaction; infusion interruption not indicated; intervention not indicated	Increase monitoring of vital signs as medically indicated until the patient is deemed medically stable in the opinion of the Investigator.	None
Grade 2: Requires infusion interruption but responds promptly to symptomatic treatment (e.g., antihistamines, NSAIDS, narcotics, IV fluids); prophylactic medications	Stop Infusion and monitor symptoms. Additional appropriate medical therapy may include but is not limited to:	Patient may be pre-medicated 1.5h ( $\pm$ 30 minutes) prior to infusion of pembrolizumab (MK-3475) with:  Diphenhydramine 50 mg po (or

NCI CTCAE Grade	Treatment	Premedication at subsequent dosing
indicated for <=24 hrs	
 
IV fluids
 
Antihistamines
 
NSAIDS
 
Acetaminophen
 
Narcotics
 
 
Increase monitoring of vital signs as medically indicated until the patient is deemed medically stable in the opinion of the Investigator. If symptoms resolve within one hour of stopping drug infusion, the infusion may be restarted at 50% of the original infusion rate (e.g., from 100 mL/hr to 50 mL/hr). Otherwise dosing will be held until symptoms resolve and the patient should be pre-medicated for the next scheduled dose.
 
Patients who develop Grade 2 toxicity despite adequate premedication should be permanently discontinued from further trial treatment administration.
	equivalent dose of antihistamine).  Acetaminophen 500-1000 mg po (or equivalent dose of antipyretic).
Grade 3: Prolonged (i.e., not rapidly responsive to symptomatic medication and/or brief interruption of infusion); recurrence of symptoms following initial improvement; hospitalization indicated for other clinical sequelae (e.g., renal impairment, pulmonary infiltrates)  Grade 4: Life-threatening; pressor or ventilatory support indicated	
Stop Infusion.
 
Additional appropriate medical therapy may include but is not limited to:
 
 
IV fluids
 
Antihistamines
 
NSAIDS
 
Acetaminophen
 
Narcotics
 
Oxygen
 
Pressors
 
Corticosteroids
 
Epinephrine
 
 
Increase monitoring of vital signs as medically indicated until the patient is deemed medically stable in the opinion of the Investigator. Hospitalization may be indicated.
 
Patient is permanently discontinued from further trial treatment administration.
	No subsequent dosing
Appropriate resuscitation equipment should be available in the room and a physician readily available during the period of drug administration.		

## 6.13 Diet, Activity and Other Considerations

### 6.13.1 Diet

Patients should maintain a normal diet unless modifications are required to manage an AE such as diarrhea, nausea or vomiting.

## 6.14 Contraception

Pembrolizumab and BGB324 may have adverse effects on a fetus in utero. Furthermore, it is not known if pembrolizumab has transient AEs on the composition of sperm.

For this trial, male patients will be considered to be of non-reproductive potential if they have azoospermia (whether due to having had a vasectomy or due to an underlying medical condition).

Female patients will be considered of non-reproductive potential if they are either:

- postmenopausal (defined as at least 12 months with no menses without an alternative medical cause; in women <45 years of age a high FSH level in the postmenopausal range may be used to confirm a post-menopausal state in women not using hormonal contraception or hormonal replacement therapy. In the absence of 12 months of amenorrhea, a single FSH measurement is insufficient.);

*OR*

- have had a hysterectomy and/or bilateral oophorectomy, bilateral salpingectomy or bilateral tubal ligation/occlusion, at least 6 weeks prior to screening;

*OR*

- has a congenital or acquired condition that prevents childbearing.

Female and male patients of reproductive potential must agree use highly effective methods of contraception while receiving study drug and for 120 days after the last dose of study drug by complying with one of the following highly effective methods‡:

- intrauterine device (IUD);
- intrauterine hormone-releasing system (IUS);
- bilateral tubal occlusion;
- vasectomized partner;
- practice abstinence from heterosexual activity†

Note: hormonal contraceptives are normally contraindicated in female patients with breast cancer.

†Abstinence (relative to heterosexual activity) can be used as the sole method of contraception if it is consistently employed as the patient's preferred and usual lifestyle and if considered acceptable by local regulatory agencies and Institutional Review Board (IRB)/Institutional Ethics Committee (IECs). Periodic abstinence e.g. calendar, ovulation, sympto-thermal, post-ovulation methods, etc. and withdrawal are not acceptable methods of contraception.

‡If a contraceptive method listed above is restricted by local regulations/guidelines, then it does not qualify as an acceptable method of contraception for patients participating at sites in this country/region.

Patients should be informed that taking the study medication may involve unknown risks to the foetus (unborn baby) if pregnancy were to occur during the study. In order to participate in the study, patients of childbearing potential must adhere to the contraception requirement (described above) from the day of study medication initiation (or 14 days prior to the initiation of study medication for oral contraception) throughout the study period up to 120 days after the last dose of trial therapy. If there is any question that a patient of childbearing potential will not reliably comply with the requirements for contraception, that patient should not be entered into the study.

#### **6.14.1 Use in pregnancy**

If a patient inadvertently becomes pregnant while on treatment with study medication, the patient will immediately be removed from the study. The site will contact the patient at least monthly and document the patient's status until the pregnancy has been completed or terminated. The outcome of the pregnancy will be reported to the Sponsor without delay and within 24 hours if the outcome is a serious adverse experience e.g. death, abortion, congenital anomaly, or other disabling or life-threatening complication to the mother or newborn. The study Investigator will make every effort to obtain permission to follow the outcome of the pregnancy and report the condition of the fetus or newborn to the Sponsor.

#### **6.14.2 Use in nursing women**

It is unknown whether pembrolizumab is excreted in human milk. Since many drugs are excreted in human milk, and because of the potential for serious adverse reactions in the nursing infant, patients who are breast-feeding are not eligible for enrolment.

## 7 ADVERSE EVENTS AND REPORTING REQUIREMENT

### 7.1 Assessment of Safety

Progression of the cancer under study is not considered an AE unless it is considered to be drug-related by the investigator.

All **AEs that occur after the consent form is signed but before treatment allocation** must be reported by the investigator if they cause the patient to be excluded from the trial, or are the result of a protocol-specified intervention, including but not limited to washout or discontinuation of usual therapy, diet, placebo treatment or a procedure.

**From the time of treatment allocation through 30 days following cessation of treatment, all AEs must be reported by the investigator.** Such events will be recorded at each examination on the Adverse Event case report forms/worksheets.

The reporting timeframe for AEs meeting any serious criteria is described in [Section 7.4.3](#). The investigator will make every attempt to follow all patients with non-serious adverse events for outcome. **From the time of treatment allocation through 90 days following cessation of treatment, all SAEs (including serious events of special interest) must be reported by the investigator.** Where a patient has initiated a new cancer treatment, the time period is 30 days after cessation of treatment. See [Section 7.4.3.1](#) and [Section 7.4.3.2](#).

The reporting timeframe for a new pregnancy is described in [Section 7.5](#).

### 7.2 Adverse Event Definition

An AE is any untoward medical occurrence in a patient or clinical study subject administered a pharmaceutical product and which does not necessarily have a causal relationship with the product. An AE can therefore be any unfavorable or unintended sign, symptom or disease temporally associated with the use of the IMP whether or not considered related to the IMP. This includes any occurrence that is new, an exacerbation of an existing disease (a worsening of the character, frequency or severity of a known condition) or abnormal results of diagnostic procedures, including clinically significant laboratory test abnormalities.

Suggested criteria for the assessment of clinical significance for laboratory abnormalities are as follows.

The laboratory abnormality:

- is clearly consistent with the pattern of the patient's underlying disease or disease progression;
- is accompanied by clinical symptoms;
- requires study drug dose modification or interruption or permanent discontinuation of study treatment;
- requires more frequent follow-up assessments, further diagnostic investigation, etc.;
- requires a change in concomitant medication, therapy, or treatment.

If the clinically significant laboratory abnormality is a sign of a disease or syndrome (e.g. alkaline phosphatase and bilirubin 5X ULN associated with cholecystitis), only the diagnosis (e.g. cholecystitis) needs to be recorded on the AE CRF. If the clinically significant laboratory

abnormality is not a sign of a disease or syndrome, the abnormality itself should be recorded as an AE or SAE on the CRF. If the laboratory abnormality can be characterized by a precise clinical term, the clinical term should be recorded as the AE or SAE. For example, an elevated serum potassium level of 7.0 mEq/L should be recorded as “hyperkalemia.” Observations of the same clinically significant laboratory abnormality from visit to visit should not be repeatedly recorded as AEs or SAEs on the CRF, unless their severity, seriousness, or etiology changes.

For all AEs, a diagnosis should be recorded on the CRF rather than individual signs and symptoms (e.g. record only liver failure or hepatitis rather than jaundice, asterixis, and elevated transaminases) wherever possible. However, if a constellation of signs and/or symptoms cannot be medically characterized as a single syndrome at the time of reporting, each individual sign and/or symptom should be recorded as an AE or SAE on the CRF. If a diagnosis is subsequently established, the reported event term should be updated to reflect the medical diagnosis.

Note that AEs occurring secondary to an initiating event that are separated in time or medically significant should be recorded as independent events on the CRF. For example, if a severe gastrointestinal hemorrhage leads to a renal failure, both events should be recorded separately on the CRF.

A pre-existing medical condition which is present at the start of the study and described in the Medical History CRF, should only be recorded as an AE or SAE if the frequency, severity, or character of the condition worsens during the study. When recording such events on the AE CRF, it is important to convey the concept that the pre-existing condition has changed by including applicable descriptors (e.g. “more frequent headaches”).

Surgical procedures or other therapeutic interventions themselves are not AEs, but the condition for which the surgery/intervention is required is an AE and should be documented accordingly.

Planned surgical measures and the condition(s) leading to these measures are not AEs, if the condition(s) was (were) known before the period of observation and did not worsen during study. In the latter case, the condition should be reported as medical history.

During clinical trials, AEs can be spontaneously reported or elicited during open-ended questioning, examination, or evaluation of a patient. To prevent reporting bias, patients should not be questioned regarding the specific occurrence of one or more AEs.

Symptoms and signs of exacerbation or worsening of the patient’s primary disease will not be captured as AEs. Progression of the disease under study (i.e. TNBC) will not be captured as an AE unless it is considered to be drug-related by the Investigator.

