### 5.3.6 Clinical chemistry, hematology, coagulation and urinalysis

Blood and urine samples for determination of clinical chemistry, hematology, coagulation and urinalysis parameters will be taken at the times given in Schedule of Study Assessment [Table 4](#) and [Table 5](#) and prior to administration of study treatment. The date and time of collection will be recorded in the source data and on the CRF.

All testing will be performed at each site's local laboratory. Coagulation parameters may be assessed from the hematology sample.

Copies of laboratory accreditation certificates and reference ranges will be obtained from each study site prior to the analysis of their first patient sample.

The laboratory variables to be measured are described in [Appendix E](#).

If any clinically significant findings are identified from the safety lab assessments, the Investigator will record it as part of the medical history prior to start of dosing and as an AE post dose, where the finding represents a change from baseline. Findings identified prior to start of dosing must be checked against the study inclusion and exclusion criteria ([Section 3.1](#) and [Section 3.2](#)).

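### Section 7.2's first suggested criterion for a clinically significant laboratory abnormality contradicts the rule that worsening disease is not recorded as an adverse event

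*Protocol*

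**What the plan says.** Protocol Section 7.2 includes in its AE definition "abnormal results of diagnostic procedures, including clinically significant laboratory test abnormalities". It then introduces a list: "Suggested criteria for the assessment of clinical significance for laboratory abnormalities are as follows". The first of the five bullets is that the abnormality "is clearly consistent with the pattern of the patient's underlying disease or disease progression". The other four concern accompanying symptoms, a change to study drug, added follow-up or work-up ("requires more frequent follow-up assessments, further diagnostic investigation, etc"), and a change in other treatment. Nothing says whether one bullet is enough or all are needed.

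Section 5.3.6 puts this into practice for safety laboratory tests: the investigator records a clinically significant finding "as an AE post dose, where the finding represents a change from baseline".

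The exclusion appears twice. Section 7.1 states: "Progression of the cancer under study is not considered an AE unless it is considered to be drug-related by the investigator". The last paragraph of Section 7.2 says that symptoms and signs of worsening of the patient's "primary disease will not be captured as AEs", and adds: "Progression of the disease under study (i.e. TNBC) will not be captured as an AE unless" the investigator considers it drug-related.

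**The concern.** The bullet and the exclusion send the same laboratory value in opposite directions. If a value clearly fits the cancer or its progression, the bullet makes it clinically significant and therefore an AE. The exclusion says it is not to be captured.

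The number and frequency of AEs is a secondary endpoint (Table 9). The trial has one arm, so there is no comparator in which disease-driven laboratory AEs would appear at a similar rate and show themselves as background. Such changes are foreseeable, because patients with liver metastases may enter with ALT and AST up to 5 times the upper limit of normal (Section 3.1, criterion 10d). Chemistry and hematology are sampled repeatedly in Cycle 1 and then every 3 weeks for up to 35 cycles, at up to approximately 20 sites. The Data Review Committee also sees AEs and laboratory results during the safety run-in (Section 4.1), for a combination not previously given to patients.

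**Working it through.** No arithmetic applies. The check is to set the passages side by side and follow a laboratory value through them.

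**Does clinical significance lead to an AE?** Yes. The AE definition in Section 7.2 and the recording instruction in Section 5.3.6 both say so. The bullet list therefore decides what is recorded.

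**Does either reading of the list avoid the conflict?**
- If any one bullet suffices, a value that clearly fits progression is clinically significant on the first bullet alone, and so an AE. Section 7.1 and the end of Section 7.2 exclude it.
- If all five are required, a value that does not fit the cancer can never be clinically significant. That would remove the values most relevant to drug toxicity and cannot be intended.

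Neither reading works.

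**Could the bullet be meant for the drug-related exception?** The exclusion of progression has such an exception, but the bullet does not mention drug relationship. It covers any value that fits the disease.

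**What happens to four kinds of post-dose value, if any one bullet suffices?**

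| Value | Bullet list | Exclusion (7.1, end of 7.2) | Result |
|---|---|---|---|
| Fits the cancer or progression, no symptoms, no action | Significant, by the first bullet only | Not captured | Direct conflict, created by the first bullet |
| Fits the cancer or progression, needs action | Significant, by the first and another bullet | Not captured, unless it reflects progression considered drug-related | General rule against a specific exclusion; the first bullet points the wrong way |
| Not explained by the cancer, symptoms or action | Significant, by bullets 2 to 5 | Does not apply | Captured, no conflict |
| Not explained by the cancer, no symptoms, no action | No bullet applies | Does not apply | No AE suggested; value still graded and listed (Section 8.12.1.2) |

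The first row is the defect. The third shows that most unexplained abnormalities of concern are still recorded. The fourth is the only unexplained group that the list leaves out.

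**Does the rule to record only the diagnosis settle it?** Section 7.2 says that when a significant laboratory value is a sign of a disease, the diagnosis is recorded instead. Here the diagnosis is progression, which the same section says not to capture. This softens the conflict in clear cases, because a careful reader arrives at no AE. It does not explain why the first bullet makes such a value reportable to begin with.

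**The case against.** The strongest reply is that the list is only suggested, whereas the exclusion is a flat rule stated in Section 7.1 and again at the end of Section 7.2. Read with the diagnosis rule, Section 7 does give an answer for disease-driven values. This lowers the likelihood and size of the harm. It does not remove the conflict, since suggested criteria are what sites are given to apply. That sites will in fact differ is a reasonable expectation, not something the protocol demonstrates.

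A second reply is that laboratory safety does not depend on this bullet. All laboratory values are graded or classified, summarized by visit, shown in shift tables and listed, with a separate listing of abnormal values (Section 8.12.1.2). Safety laboratory parameters are named in the same secondary endpoint as AEs (Table 9). The combined transaminase and bilirubin criterion is a separately reportable event of clinical interest (Section 7.4.3.2). Every AE is assessed for relationship to both drugs (Section 7.4.2) and tabulated by it (Section 8.12.1.1). The run-in thresholds count dose reductions and discontinuations, not AEs (Section 8.2.1). All of this stands and limits the consequence to AE recording.

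A reader might infer that the list omits abnormalities not explained by the cancer, so that drug or immune toxicity would go unrecorded. The protocol does not support that. Bullets 2 to 5 do not depend on cause, and an unexplained liver or renal rise of concern would ordinarily prompt repeat testing or work-up, which the fourth bullet covers.

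A reader might also infer that a 'not' was dropped and that restoring it is the whole remedy. The omission is plausible but is an inference. If any one bullet suffices, the bare negation would make every trivial out-of-range value not attributable to the cancer clinically significant, and so an AE.

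**Conclusion.** The contradiction is in the current text and holds under either reading of the list. Followed as written, the first bullet can add disease-driven laboratory AEs to the AE secondary endpoint and lead to inconsistent recording between sites. The protocol gives no rate from which to estimate how many.

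The effect is limited to AE recording and counts. Unexplained abnormalities with symptoms or action are still captured, laboratory data are reported separately, and the primary objective response analysis is unaffected. The conclusion that AE counts would change assumes that at least some sites apply the suggested criteria as printed; the contradiction itself needs no assumption. It is an inexpensive correction worth making, not a threat to the trial's main conclusion.

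**What to change.** Reconcile the first bullet in Section 7.2 with Section 7.1 and the last paragraph of Section 7.2, in one of two ways:

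1. Delete the bullet and cross-refer to the progression exclusion at the head of the list.
2. Reword it so that it applies to an abnormality that is not clearly consistent with the underlying disease or its progression and that the investigator judges clinically significant. The second condition keeps trivial out-of-range values from qualifying.

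Under either option, state that meeting any one criterion suffices, and align the eCRF completion guidance. A cross-reference to the exclusion helps with the second option too, because a progression-driven value that needs extra follow-up still meets the fourth bullet.

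The cost is a small wording change in the protocol and the guidance, with no added assessments. The second option may bring a few more low-grade laboratory AEs.

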### 7.4.2 Assessment of relationship

All AEs (including SAEs) will be assessed for the relationship of the AE to both pembrolizumab and BGB324 study drug using the following definitions:

- **Not/unlikely related** - The AE is not related if exposure to the investigational product has not occurred, *OR* the occurrence of the AE is not reasonably related in time, *OR* the AE is considered unlikely to be related to use of the investigational product because there are no facts (evidence) or arguments to suggest a causal relationship *AND* there is a possible alternative explanation.
- **Possibly related** - The administration of the investigational product and AE are considered reasonably related in time *AND* the AE could be explained by causes other than exposure to the investigational product.

- **Probably related** - Exposure to the investigational product and AE are reasonably related in time *AND* the investigational product is more likely than other causes to be responsible for the AE *OR* is the most likely cause of the AE.
- **Definitely related** - There is a reasonable temporal sequence between exposure to the investigational product and the AE, *OR* the event follows a known or expected response pattern to the investigational product, *AND* is confirmed by improvement on stopping the dosage of the investigational product. It may also be confirmed by reappearance upon repeated exposure where this is medically and ethically acceptable.

The relationship of the study treatment to an AE will be determined by the Investigator and subsequently reviewed by the Medical Monitor.

For reporting and data analysis purposes, AEs reported with a causality assessment of “Definitely”, “Probably”, and “Possibly” are to be considered as “having a reasonable causal relationship” to study drug. In case of disagreement between the Investigator and the Sponsor’s Medical Monitor, the more conservative assessment will determine the reportability of the case.

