- Absence of signs and symptoms indicating disease progression;
- No decline in ECOG PS;
- Absence of rapid progression of disease;
- Absence of progressive tumor at critical anatomical sites (e.g., cord compression) requiring urgent alternative medical intervention.

When feasible, patients should not be discontinued from their study treatment until progression is confirmed. This allowance to continue treatment despite initial radiologic progression takes into account the observation that some patients can have a transient tumor flare in the first few months after the start of immunotherapy, but with subsequent disease response. Patients that are deemed clinically unstable are not required to have repeat imaging for confirmation of progressive disease.

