### **10.3 Informed Consent**

The principles of informed consent in the Declaration of Helsinki and GCP guidelines will be implemented before any protocol-specific procedures or interventions are carried out.

All patients will be informed that participation is voluntary and that they can cease their study treatment(s) and/or their further participation to any further study assessments at any time without necessarily giving a reason and without any penalty or loss of benefits to which they are entitled.

Patients will be provided with two consent forms prior to the commencement of any procedures or investigations:

- i. The Main Consent to participate in the study will include information about the patient's disease, alternative treatment options, the study treatments and their duration, study design and study assessments and procedures, risks, side effects and potential benefits of participation. This consent will include:
  - a. Consent to provide sufficient tumor tissue to enable Axl kinase and PD-L1 expression measurement by IHC, and an explanation that this includes the provision of a newly acquired tumor tissue sample.
  - b. If possible, the electronic storage of all radiological and non-radiological scans at site for future reference (e.g. medical case studies, publications and training).

- c. Information regarding the expected (maximum) blood volume to be provided.
- d. Information that treatment with checkpoint inhibitors, such as pembrolizumab, is occasionally associated with worsening of disease before clinical improvement is observed. Therefore, their treatment may continue if their doctor suspects that the patient is benefiting from the treatment.
- e. Information that treatment with checkpoint inhibitors, such as pembrolizumab, and treatment with BGB324 are associated with side effects and that the patient must inform the doctor of any side effects, even if the patient does not think they are important.
- f. An explanation that patients will continue to have 12 weekly follow-up visits (or in some cases, a telephone call) to assess their disease and/or well-being after the completion of their study treatments. Follow-up visits or telephone contact will continue until the end of the study.
- g. Information to explain that on-study blood samples will be collected for the purpose of assessing biomarkers of Axl signaling and inhibition.

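### Section 7.2 excludes symptoms and signs of worsening disease from the AE record without the drug-related exception that it and Section 7.1 give to progression, so non-serious symptoms of an immune-related flare have no clear recording rule

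*Protocol*

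**What the plan says.** The last paragraph of Protocol Section 7.2 contains two consecutive rules. The first is unqualified: "Symptoms and signs of exacerbation or worsening of the patient’s primary disease will not be captured as AEs". The second says that progression of TNBC "will not be captured as an AE unless it is considered to be drug-related by the Investigator". Where the two meet, the text runs "primary disease will not be captured as AEs. Progression of the disease under study (i.e. TNBC) will not be captured as an AE unless", and the exception that follows belongs to the second rule alone. Section 7.1 repeats the exception, again for progression only: "Progression of the cancer under study is not considered an AE unless it is considered to be drug-related by the investigator".

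The general definition at the start of Section 7.2 counts as an AE "an exacerbation of an existing disease (a worsening of the character, frequency or severity of a known condition"), whether or not it is thought related to the product.

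On worsening under immunotherapy, Section 8.5.1 notes that "some patients can have a transient tumor flare in the first few months after the start of immunotherapy", followed by response. Section 10.3 requires the consent form to say that treatment with checkpoint inhibitors such as pembrolizumab "is occasionally associated with worsening of disease before clinical improvement is observed". The Synopsis (Study Design, text after Table 2) asks for a confirmatory scan to rule out apparent progression that is really an inflammatory immune response.

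The number and frequency of adverse events belong to the secondary safety endpoint (Table 1 and Table 9).

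**The concern.** The sponsor has already accepted that worsening of the cancer should be recorded when the Investigator thinks the drug is responsible. That principle is written into the progression rule but not into the rule on symptoms and signs beside it. The gap matters for one kind of event: temporary worsening that the Investigator suspects is due to treatment but that is not progression. The protocol itself describes such an event.

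At stake is the completeness and consistency of AE capture in a single-arm study of a combination that, according to Section 4.1, had not been given to patients before. Up to approximately 20 sites would have to interpret the two sentences. Section 7.4.2 provides a second look at causality ("The relationship of the study treatment to an AE will be determined by the Investigator and subsequently reviewed by the Medical Monitor"), but it applies to AEs, so a symptom that is never entered as an AE does not reach it.

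**Working it through.** No arithmetic applies. The protocol gives no flare rate and no count that depends on this rule, so the check is a comparison of texts.

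1. **Do the two rules differ?** Yes. The exception is attached to progression in Section 7.2 and in Section 7.1. In neither place is it attached to symptoms and signs.

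2. **Could the progression exception cover flare?** Not clearly. The Synopsis describes the event as pseudo or false progression. Sections 4.1 and 8.11 speak of a wrong categorization as progression and allow later scans to be used for the response assessment. Section 8.5.1 describes a flare with later response. An Investigator who recorded such an event as drug-related progression would be using a label that these sections tell them to doubt. What remains is the unqualified sentence.

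3. **Does the rule preferring a diagnosis over individual symptoms resolve it?** No. In Section 7.2 that rule is framed for all AEs. It governs how an AE is named, not whether an excluded symptom becomes one.

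4. **Does the general definition resolve it?** No. It would include worsening of an existing disease, but the closing paragraph is the more specific text and would normally prevail. Section 7.2 also lists, as its first suggested criterion for a clinically significant laboratory abnormality, that the finding fits the pattern of the underlying disease or its progression. A laboratory sign of worsening cancer is thus pointed towards the AE record in one part of the section and away from it in another.

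5. **Which routes remain open?**
   - Worsening that the Investigator calls progression and considers drug-related can be recorded (Sections 7.1 and 7.2).
   - Serious events must be reported whether or not related. The exclusion that Section 7.4.3.1 names is death from progression of the study cancer.
   - Laboratory values, vital signs and ECGs are collected in their own right.
   - Dose reductions and permanent discontinuations go to the DRC. The run-in thresholds in Section 8.2.1 (4 or more of 6 patients, 5 or more of 12) count those actions, not AE entries.

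6. **What is left?** Non-serious symptoms or signs of temporary worsening that is not called progression and that the Investigator suspects is drug-related. Taken literally, the text excludes them; taken by its evident intent, it would include them.

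**The case against.** The strongest reply is that the two sentences were meant to work together: disease symptoms are not itemised, and the overall diagnosis of worsening is recorded when the drug is suspected. On that reading a general definition is followed by a deliberate exception. This is a plausible account of the intent and explains why the point is small. It does not settle flare, because the only diagnosis carrying the exception is progression, and the protocol distinguishes flare from true progression.

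A second reply is that Section 8.5.1 is about imaging. It lets patients continue while progression awaits confirmation only if they are clinically stable, without symptoms or signs of progression and without decline in ECOG status. Few symptoms may therefore be lost. This stands as a limit on size. Those criteria decide who may stay on treatment, however; they do not say how symptoms are recorded, and the consent text speaks of worsening of disease without restricting it to scans.

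Three stronger readings are tempting and are not supported:

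- A reader might infer that a known drug effect is left out of the safety endpoint altogether. The routes for drug-related progression and serious events contradict that. The protocol also reports an observation and an occasional association, which is weaker than saying that pembrolizumab causes symptomatic flare.
- A reader might infer that toxicity mistaken for cancer, such as rash taken for inflammatory breast disease, disappears from the tables. That is a different problem. An event attributed wholly to the cancer would go unrecorded under the amended wording too, so it is no argument for this change.
- A reader might want a number of missing patients. Any flare rate would have to be invented, and a count would further assume that every case goes unrecorded.

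**Conclusion.** The point holds as a minor correction. The unqualified sentence in Section 7.2 does not match the progression rule beside it or Section 7.1, and the mismatch falls on a type of event that the protocol describes. The consequence is omission or inconsistent recording of non-serious symptoms and signs that the Investigator suspects are drug-related. It does not affect ORR, the interim or final decision boundaries, or the run-in thresholds.

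The conclusion assumes that sites apply the sentence as written and do not call flare progression. If they treat flare as drug-related progression, the events are captured, but under a label at odds with Section 8.5.1. The size cannot be derived from the protocol.

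**What to change.** Give the symptoms-and-signs sentence in Section 7.2 the exception already accepted for progression. Suggested wording: *symptoms and signs of worsening primary disease are not captured as AEs unless the Investigator considers them at least possibly related to BGB324 or pembrolizumab.* Repeat it in Section 7.1. The threshold fits Section 7.4.2, where possible, probable and definite relationship already count as a reasonable causal relationship, and events recorded this way then receive the Medical Monitor's review.

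The cost is one clause in two sections and a few additional AE records, some of which will turn out to be disease. No treatment rule, visit or analysis method changes.
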